TAM	Tumour Associated Macrophage

KEYWORDS

Tumour, Oxygenation, Sensor, Diffuse Reflectance Spectroscopy

STUDY SUMMARY

TITLE	Development and Validation of a Tumour Oxygenation Monitoring Probe
DESIGN	Tumour oxygenation sensor validation using 3D-Printed tissue phantoms
AIMS	To design and validate a novel tumour oxygenation monitoring probe which may be used to monitor response to therapies in cancer, using 3D-printed phantoms
OUTCOME MEASURES	Correlation of sensor oxygenation measurements as compared to gold-standard oxygenation measurements in phantom tissue models
POPULATION	3D printed tissue phantoms, based upon breast and rectal cancer MRIs
ELIGIBILITY	20 Anonymised pre-treatment MRI scans for patients with locally advanced rectal cancer (10 scans) and breast cancer (10 scans) MRIs from patients younger than 18 years of age, or older than 99 years of age will be excluded. MRIs from patient who did not go on to receive neoadjuvant therapy will be excluded
DURATION	1 Year

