1.1.4 Tissue Oxygenation Monitoring Using Diffuse Reflectance Spectroscopy

Diffuse reflectance spectroscopy can measure the oxygenation status of tissue due to the differing absorbance profiles of oxygenated and deoxygenated haemoglobin (Figure 1A). DRS is well suited to oxygenation monitoring as it provides oxygenation measurements that are dynamic (real-time), spatially accurate and quantifiable. Furthermore, it has the potential to be miniaturized into an implantable device.

[figure not shown]

Figure 1: Optical absorbance of oxygenated and deoxygenated haemoglobin.

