1.2 RATIONALE FOR CURRENT STUDY

Overall Research Hypothesis:

- Dynamic tumour oxygenation monitoring can predict treatment response in chemoradiotherapy for rectal and breast cancer.

Current Research Hypothesis:

- A novel-designed tumour oxygenation monitor, utilising diffuse reflectance spectroscopy, can provide accurate tissue oxygenation assessment in tumour phantom models.

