2. STUDY OBJECTIVES

Primary Objective:

- To develop and validate a novel tumour oxygenation monitoring probe which may be used to monitor response to therapies in cancer, using 3D-printed phantoms.

Secondary Objectives:

- Define the correlation between sensor-derived oxygenation measurements and Gold-standard measured oxygenation in 3D-printed tissue phantoms
- Define the spatial resolution of the sensor oxygenation measurements

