3.2 TOAST++ Simulations

The TOAST++ framework is software which models the diffuse light transport in tissue, which first requires a Finite Element Mesh of the target issue [8]. These meshes will be constructed based upon the requested anonymised MRI segmentations. Optical signals will be simulated for a variety of sensor/probe/implant designs for a range of tissue parameters, based on scattering and absorption values from the literature [9]. These simulations will be used to initially verify the extent of sensitive volume within the tumours, allowing for optimisation of the sensor-detector spacing. Then hypoxic regions will be simulated based on distributions from the literature and any potential candidates from the MRIs. These simulations will demonstrate the sensitivity of the sensor to changes in oxygenation.

3.3 3D-Printing of Phantoms

Prototype sensor designs will be verified in experiments using phantoms with realistic geometry, based on the same meshes of the MRI segmentations used simulations. The tissue phantoms will be 3D printed tissue phantoms will be produced according to the methodology described by *Dempsey et al.* First the tumour segmentations will be converted to 3D surfaces in standard tessellation language (STL) file format. The phantoms will be printed using a Formlabs 3D printer, using resin containing titanium oxide and near-infrared (NIR) dye (Projet 900NP) so as to mimic tissue absorption and scattering properties.

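### As listed in Section 3.3, the phantoms carry one dye and no set oxygenation levels; unless the cited printing method supplies levels, the sensor-versus-benchtop correlation cannot support the Section 1.2 accuracy hypothesis

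*Combined protocol and SAP*

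**What the plan says.** All references are to the combined protocol and SAP.

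- **Basis of the reading (1.1.4).** Diffuse reflectance spectroscopy measures oxygenation "due to the differing absorbance profiles of oxygenated and deoxygenated haemoglobin".
- **Phantom material (3.3).** The phantoms are printed "using resin containing titanium oxide and near-infrared (NIR) dye (Projet 900NP) so as to mimic tissue absorption and scattering properties". Production follows a cited published method. No second absorber, dye concentration or oxygenation level is stated.
- **Where oxygenation varies (3.2).** "Then hypoxic regions will be simulated based on distributions from the literature", and "These simulations will demonstrate the sensitivity of the sensor to changes in oxygenation". This concerns the TOAST++ model, not the printed objects.
- **Reference (3.4).** A benchtop spectrometer reads oxygenation in the same phantoms and is called the gold standard. The results are to judge whether the sensor suits oxygenation monitoring in tumours.
- **Hypothesis (1.2).** The monitor "can provide accurate tissue oxygenation assessment in tumour phantom models".
- **Outcome (Study Summary).** "Correlation of sensor oxygenation measurements as compared to gold-standard oxygenation measurements in phantom tissue models".
- **Objectives (2).** Primary: "To develop and validate a novel tumour oxygenation monitoring probe". One secondary objective is "Define the correlation between sensor-derived oxygenation measurements and Gold-standard measured oxygenation in 3D-printed tissue phantoms"; the other is the spatial resolution of the oxygenation readings.
- **Analysis (3.5).** Only the fraction of tumour volume to which the sensor is sensitive, summarised as mean and SD.

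**The concern.** A correlation is informative only if the quantity being measured varies, and a validation of accuracy also needs a known or independently measured truth. As listed, nothing in the phantoms makes oxygenation vary, and no value is assigned to any phantom. The reference is a second optical instrument reading the same object, so both devices may respond to the same geometry or scattering effects.

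The correlation is the only outcome measure in the Study Summary and the evidence offered for the current hypothesis. Section 1.1.5 makes successful validation the step before miniaturising the technology into an implantable device, and Section 7 plans a validation paper. A coefficient that does not bear on oxygenation would carry forward into both. If the phantoms are printed without an oxygenation range, no later analysis can recover one.

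**Working it through.** The plan gives no expected correlation, variance or sample-size calculation, so there is no figure of its own to reproduce. The check sets the sections side by side and then illustrates the consequence.

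**1. Counts from the documents.** Spectra behind the reading: 2 (1.1.4). Absorbers listed for the phantoms: 1 (3.3). Oxygenation levels stated for the phantoms: 0. Correlation or agreement analyses in 3.5: 0. Source scans: 20 (Study Summary). Number of phantoms: not stated.

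**2. Does varying the dye concentration create an oxygenation range?** Let E be the 2×2 extinction matrix of the two haemoglobins, d the dye's absorbance at two wavelengths and c its concentration. Linear unmixing gives x = E⁻¹(c·d) = c·E⁻¹d. Apparent saturation is x₁/(x₁+x₂), in which c cancels. Trials with three arbitrary extinction sets at 0.5, 1, 2 and 4 times the dye gave one constant value per set. Any departure from linearity would be an optical effect, not oxygenation.

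**3. What r would be with no oxygenation spread.** Assumptions, none from the documents: sensor error SD a = 5 saturation points, benchtop error SD b = 2, artefact SD s in each device, and correlation ρ between the two devices' artefacts.

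r = ρs² / √[(s²+a²)(s²+b²)]

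- s = 0: r = 0.00.
- s = 5, ρ = 1: 25/√(50×29) = 25/38.08 = 0.66. With ρ = 0.5: 0.33.
- s = 10, ρ = 1: 100/√(125×104) = 100/114.02 = 0.88. With ρ = 0.5: 0.44.

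With 20 phantoms (one per scan, assumed) and s = 0, the 95% range of the observed r is ±tanh(1.96/√17) = ±0.44.

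**4. What r would be with a real spread.** With no artefact and the same error SD e in each device, r = T²/(T²+e²), where T is the SD of true oxygenation across phantoms. At e = 5, T = 2, 5, 10 and 20 give 0.14, 0.50, 0.80 and 0.94. At e = 3 they give 0.31, 0.74, 0.92 and 0.98. The coefficient depends heavily on a spread that the plan does not state.

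**5. Correlation against accuracy.** A sensor reading 0.5 × true + 30 has r = 1.00 with the truth. At true 20 it reads 40 (error +20); at true 90 it reads 75 (error −15). This holds whatever the phantoms are made of.

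**6. What agreement can detect.** The SD of sensor minus benchtop is √(a²+b²+2s²(1−ρ)).

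- ρ = 1: √29 = 5.4 at every s, so fully shared artefact is invisible.
- ρ = 0.5: √54 = 7.3 at s = 5 and √129 = 11.4 at s = 10, so partly shared artefact shows in part.
- Against a known formulated level the SD is √(s²+a²): √50 = 7.1 at s = 5 and √125 = 11.2 at s = 10. The artefact shows in full.

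**7. Precision of an agreement analysis.** 95% CI half-widths, in units of the SD of the differences, are t/√n for bias and t·√(1/n + 1.96²/(2(n−1))) for each limit. For n = 20, t = 2.093: 0.47 and 0.81. For n = 10: 0.72 and 1.27. For n = 40: 0.32 and 0.55.

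**The case against.** The strongest reply is that the premise is an omission. Section 3.3 defers production to a cited method, and its sentence on the resin states a purpose without saying that the list is complete or that all prints share one formulation. The method may provide several absorbers, inclusions or graded levels. This stands, and it makes the conclusion conditional. A reader might infer that the phantoms are known to hold no oxygenation contrast, or that the validation has been shown to fail; the documents do not support either. They do show that the protocol itself gives no oxygenation range or assigned value, although its outcome depends on one.

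A second reply is that the illustration assumes exactly zero oxygenation spread and, in its larger figures, artefact that enters both devices identically. Section 3.4 says the devices differ spectrally, so full sharing may be too strong. This also stands: at ρ = 0.5 the coefficients halve. The figures show that r can be high or low without an oxygenation signal; they do not predict what r will be.

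A third reply is that the simulations cover oxygenation. They do vary it, but they do not test the physical sensor against the benchtop reference, which is what the Summary, 1.2 and Section 2 promise.

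Finally, the gap in 3.5 is a separate omission. It holds whatever the phantom material and adds no certainty about that material.

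**Conclusion.** The point holds conditionally, and should be settled before printing. For the phantoms as listed in 3.3, the oxygenation correlation has neither a defined range nor a known truth, and cannot support the 1.2 hypothesis. If the cited method sets oxygenation-equivalent levels, the fault reduces to their absence from the protocol and from the analysis. In either case correlation alone does not show accuracy, and 3.5 contains no analysis of the stated outcome.

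The size that rests on the documents is the mismatch itself: one listed absorber against two spectra, no stated levels and no planned correlation or agreement analysis. The range of r from 0.00 to 0.88 rests on assumed SDs and zero oxygenation spread.

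It would go too far to conclude that the phantom work has no value. Section 3.3 presents the phantoms as a realistic-geometry check of prototype designs, and comparing a few-wavelength sensor with a broadband spectrometer remains a useful device comparison.

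**What to change.** Choose one of two routes before printing; they are of equal standing.

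**Route A (keeps the 1.2 hypothesis).** State in 3.3 the absorbers and the known oxygenation-equivalent levels of the phantoms, whether they come from the cited method or from added reference prints. Add to 3.5: *For the sensor against the formulated level, the mean difference and 95% limits of agreement will be reported with 95% CIs, with the phantom as the unit of analysis.* If the cited method already sets levels, the cost is wording. New prints cost resin formulation and laboratory time, but need no further patient scans.

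**Route B (same phantoms and readings).**
- Restate the Summary outcome and the Section 2 correlation objective as agreement between sensor and benchtop on the optical signal at the sensor's wavelengths.
- Add to 3.5: *For each sensor wavelength, the mean difference (sensor minus benchtop) and 95% limits of agreement will be reported with 95% CIs, with the phantom as the unit of analysis.*
- State the number of phantoms and the dye concentrations, since agreement is shown only over that range.
- Align the Summary title and aims, 1.2, the primary objective, the spatial-resolution objective, 3.4 and Section 7, so that oxygenation response is claimed from simulation only.
- State that agreement between the devices cannot exclude artefact common to both.

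Route B costs wording and one analysis sentence. Its downside is a narrower claim. Section 5.1 records that approval is already held, so the change may need handling as an amendment.

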3.4 Sensor Measurement Collection

Measurements of oxygenation within the 3D printed phantoms will first be performed using a benchtop spectrometer to provide a “gold standard”. This benchtop system allows for measurements with a high spectral resolution over a broad spectral range, whereas the sensor by necessity is targeted at key wavelengths (Figure 1). The results of these experiments will assess the suitability of the sensor design for monitoring oxygenation in tumours.

[figure not shown]

Figure 3: Schematic demonstrating a 3D printed phantom, TOAST++ simulation, novel monitoring probe and future miniaturised device (left to right)

3.5 Statistical Analysis

The fraction of the volume of the tumour to which the sensor is sensitive will be expressed as a % of the total volume, and the fraction for each tumour will be expressed as a mean+SD summary statistic.

4. PARTICIPANT ENTRY

4.1 INCLUSION CRITERIA

10 Breast MRIs from patients identified from multidisciplinary team meeting (MDT) records who went on to have neoadjuvant chemo and hormonal therapy for locally advanced breast cancer. The MRIs will be anonymised by the care team before being made available to the research team.

10 Rectal MRIs from patients identified from MDT records who went on to have neoadjuvant radiotherapy for locally advanced rectal cancer. The MRIs will be anonymised by the care team before being made available to the research team.

4.2 EXCLUSION CRITERIA

MRIs from patients under the age of 18, or older than 99 years old will be excluded.

MRIs from patients who did not receive neoadjuvant therapy for cancer will be excluded.

5. REGULATORY ISSUES

5.1 ETHICS APPROVAL

The Study Coordination Centre has obtained approval from the Health Regulator Authority (HRA). The study will be conducted in accordance with the recommendations for physicians involved in research on human subjects adopted by the 18th World Medical Assembly, Helsinki 1964 and later revisions.

5.2 CONFIDENTIALITY

MRIs will be anonymised by the ICHNT Department of Radiology prior to transfer of data to the research team. The research team will never have access to personal identifiable information.

The Chief Investigator will preserve the confidentiality of retrospective data used in the study and is registered under the Data Protection Act.

5.3 INDEMNITY

Imperial College London holds negligent harm and non-negligent harm insurance policies which apply to this study.

5.4 SPONSOR

Imperial College London will act as the main Sponsor for this study.

5.5 FUNDING

The Biomedical Research Council are funding this study

5.6 AUDITS

The study may be subject to inspection and audit by Imperial College London under their remit as sponsor and other regulatory bodies to ensure adherence to GCP and the UK Policy Framework for Health and Social Care Research.

6. STUDY MANAGEMENT

The day-to-day management of the study will be co-ordinated by [name].

7. PUBLICATION POLICY

It is intended a peer-reviewed paper describing the development and validation of the tumour oxygenation sensor

The peer reviewed paper will be published in line with Imperial College London's open access policy.

